RESEARCH PROBLEM: Despite the “solid” evidence in favor of the effects of exercise training in breast CS to improve variables such as anxiety, depressive symptoms, fatigue, quality of life, lymphedema and physical function, however, unfortunately, the effects of exercise training on cardio-vascular and metabolic variables, there is still unknown the effects of concurrent exercise training including HIIT plus RT in lower 1RM doses in CS women at level of their cardio-vascular and metabolic health.

This is due to the fact that year after year there is an increase in the number of early diagnoses, as well as an increase in the number of CS with a successful completion of their breast cancer treatment (Radiotherapy, Chemotherapy, Hormonal Therapy), which also leads as an effect to an inherent increase in the number of CS persons, requiring the insertion of this population back into active life. Another effect of the scientific rationale lies in the scarce offer of physical activity and/or exercise training programs for this population of women between 40 and 70 years of age, which would be significantly overcome with the application of the present intervention project that would report cardiovascular, metabolic, physical condition, quality of life and eating patterns variables. **OBJECTIVES; GENERAL:** To determine the effects of traditional therapy added to physical exercise on cardio-vascular, metabolic and physical fitness in female breast cancer survivors who received lower (≤ 7 sessions) and higher (≥ 8 sessions) of chemotherapy.

This study will follow the CONSORT guidelines for randomised trials, will be developed in accordance with the Declaration of Helsinki (2013), and has been approved by the BIOETICAL COMMITTEE OF UNIVERSIDAD ANDRES BELLO (Approval 005/2024 of April 12th). **Design:** An experimental clinical randomized study. **Methods:**

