Adult women breast cancer survivors who have undergone all the stages related to breast cancer treatment (chemotherapy, radiotherapy, hormone therapy). The study will be carried out in the facilities of the Exercise Physiology Laboratory of the Exercise and Rehabilitation Sciences Institute of the Universidad Andrés Bello, Concepción city, from different community cancer survivors' social groups of the Concepcion, Chile will be invited to participate of this study. The groups will be randomly allocated to an experimental group of high chemotherapy exposure (EG-HCHT, n=15) or to an experimental group of low chemotherapy exposure (EG-LCHT, n=15), that will adhere to 6-weeks of an exercise training program of concurrent training of HIIT plus RT three weekly.

Inclusion criteria: a) breast cancer diagnosed, b) with or without chemotherapy treatment, c) normal weight body mass index [BMI] 18.6 to 24.9 or overweight/obesity condition by BMI 25.0 to 39.9 kg/m², d) age 30 to 75 years, e) with or without other associated co-morbidities (diagnosed of elevated fasting glucose, prediabetes or diabetes, hypertension or prehypertension, or metabolic syndrome, fatty liver or hypercholesterolemia or screened by our research team), f) with or without hormonal therapy, and g) with or without other pharmacotherapy for specific muscle-groups such as morphine patches, morphine droplets or other pharmacological therapy for SOS pain treatment. **Exclusion criteria:** a) history of abnormal ECG, or diagnosis of other cardiovascular condition/history other than hypertension, vasculopathy, b) history of uncontrolled stage 3 of hypertension or hypertensive crisis, c) diabetes complications such as varicose ulcers, nephropathies, d) skeletal muscle abnormalities (e.g., knee, or hip arthrosis, muscle pain), e) using weight loss treatment/pharmacotherapy or being active in exercise training programs (or within the past three months), and f) use other pharmacotherapy that can influence body weight loss, g) respiratory disease type (chronic

obstructive disease), h) kidney disease, i) pregnancy, and j) smoking behaviour or dependence on other substances.

REFERENCES

1. MINSAL. Tabla de resumen de mortalidad por causa, según sexo y región 2023 [Available from: <https://informesdeis.minsal.cl/SASVisualAnalytics/>].
2. WHO. WHO Guidelines on Physical Activity and Sedentary Behaviour. Geneva; 2021.

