
16. Cohen J. *Statistical Power Analysis for the Behavioral Sciences*. 2013.

STATISTICAL ANALYSIS PLAN (SAP): Data will be presented as the mean \pm standard deviation (SD). Normality and homoscedasticity assumptions will be tested by using Shapiro-Wilk tests and homoscedasticity by the Levene test. For those outcomes with normal distribution, paired *t*-test was applied to test differences, while to those with no normal distribution, unpaired *t*-test was applied. Cohen's *d* effect size (<0.2 = negligible, $0.2-0.49$ = small, $0.5-0.79$ = moderate, ≥ 0.8 = large) for interactions that showed statistically significant (16). Each delta (Δ), pre-post changes, of main and secondary outcomes will be calculated in all groups. To test the associations among main vascular outcomes (PWV, FMD, cIMT_{av}, cIMT_{max}) with anthropometric, body composition, metabolic, cardio-vascular outcomes, and physical fitness outcomes, simple linear regression (to parametric) with R² prediction percentage, or the *Rho* Spearman nonparametric correlation (r_s =) will be applied. Statistical analyses will be developed using Prism 8.0 software (Graph Pad, San Diego, CA, United States), and the SPSSTM software 29 version for Windows (IBM SPSS Inc., Chicago, IL, USA). The alpha level will be fixed at ($P \leq 0.05$) for all statistical significance.

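### The high versus low chemotherapy contrast is observational, hormonal therapy is left open at entry, and the SAP names no adjusted between-group analysis, so a drug difference could be read as an exposure difference.

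*Combined protocol and SAP*

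**What the plan says.** **Groups.** The general objective concerns survivors who "received lower (≤ 7 sessions) and higher (≥ 8 sessions) of chemotherapy". Methods then states: "The groups will be randomly allocated to an experimental group of high chemotherapy exposure (EG-HCHT, n=15", with a low-exposure group of the same size. Both groups follow the same 6-week concurrent programme.

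**Drug use at entry.** Inclusion criterion e) admits women "with or without other associated co-morbidities (diagnosed of elevated fasting glucose, prediabetes or diabetes, hypertension or prehypertension" and further metabolic conditions. The next criterion reads "f) with or without hormonal therapy". The drug-based exclusions cover weight-loss treatment and "use other pharmacotherapy that can influence body weight loss". Antihypertensive, lipid-lowering and hormonal drugs are named in no exclusion. The opening of Methods describes the population as women "who have undergone all the stages related to breast cancer treatment (chemotherapy, radiotherapy, hormone therapy". No stratification, matching, medication-stability rule or medication record is described.

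**Analysis.** The SAP says: "paired *t*-test was applied to test differences, while to those with no normal distribution, unpaired *t*-test was applied". Pre-post changes (Δ) are to be calculated in all groups. The remaining methods are simple linear regression of the vascular outcomes on other measured outcomes, and Spearman correlation. The SAP attaches effect sizes to significant interactions, but names no model that contains one. No covariate appears anywhere.

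**The concern.** Randomisation normally entitles a trial to an unadjusted comparison. Here the attribute that separates the groups is treatment history, so any factor associated with that history can differ between them. Hormonal therapy is one such factor that the criteria explicitly leave open. Treatment for hypertension, diabetes or raised cholesterol may be another.

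The main vascular outcomes (PWV, FMD, cIMT) and the metabolic outcomes are ones on which such drugs could plausibly act. If drug use is uneven and affects Δ, the comparison of EG-HCHT with EG-LCHT mixes the two influences. A reader of the results could not separate them, and the stated alpha of 0.05 would not be the actual error rate for a chemotherapy-exposure effect.

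**Working it through.** **Inputs from the documents:** 15 women per group; alpha 0.05 (sidedness not stated, two-sided assumed); groups defined by past sessions; no adjustment named. The 15 per group comes without power, effect size or SD, so there is no plan figure to reproduce.

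**Assumptions (the documents give no values):** drug shares in each group, and a drug effect of 0.5 to 1.0 SD, where SD is the residual SD among women with the same drug status.

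**Step 1. What a drug does to Δ.** Let D = 1 for a user. Write the pre value as a + mD and the post value as a + mD + τ + γD, where m is the drug's constant effect on level, τ the training effect, and γ any change in training response or any shift arising during the 6 weeks. Then

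- Δ = τ + γD, so m cancels;
- bias of the group difference in Δ = (p_H − p_L) × γ;
- bias if post values are compared = (p_H − p_L) × (m + γ).

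Bias in Δ therefore requires γ ≠ 0, not merely a drug that affects the vascular outcome.

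**Step 2. Error rate of the unadjusted t-test with no true exposure effect.** The true SE of the difference is √(2/15) = 0.365 residual SD. I simulated 400,000 trials per scenario with user counts fixed.

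| Users, H v L (of 15) | Gap | Bias at 0.5 / 1.0 SD | Actual error at 0.5 / 1.0 SD |
|---|---|---|---|
| 9 v 6 | 20 points | 0.10 / 0.20 | 5.1% / 5.2% |
| 10 v 5 | 33 points | 0.17 / 0.33 | 6.5% / 10.0% |
| 12 v 6 | 40 points | 0.20 / 0.40 | 7.5% / 13.7% |
| 12 v 3 | 60 points | 0.30 / 0.60 | 11.6% / 29.8% |

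Inflation is small at a 20-point gap because the drug mix within each group also widens the estimated variance. For 12 v 6 at 1.0 SD, the added variance is (15/14) × (0.8×0.2 + 0.4×0.6)/2 = 0.214, so the t-test works with an SE of about 0.365 × √1.214 = 0.402.

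**Step 3. After adding a drug term.** In a linear model with group and D, simulated error was 4.9% to 5.1% in every scenario. The SE ratio is 1/√(1 − φ²), with φ = (p_H − p_L) × 0.5/√(p̄(1 − p̄)), where p̄ is the overall share of users:

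- 9 v 6: φ = 0.20, ratio 1.02
- 10 v 5: φ = 0.33, ratio 1.06
- 12 v 6: φ = 0.41, ratio 1.10
- 12 v 3: φ = 0.60, ratio 1.25

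**Step 4. How likely are such gaps by chance alone?** If use were unrelated to exposure, with 20% to 50% of women using the drug, a gap of at least 3 of 15 has probability 0.25 to 0.36 and a gap of at least 5 of 15 has probability 0.04 to 0.10 (difference of two binomials). The larger gaps in the table would therefore mostly need a real association between exposure group and drug use.

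**The case against.** Several counter-arguments have force.

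**Current drug use is an inference.** A reader might conclude that the plan permits ongoing hormonal and cardiometabolic drugs. The text does not go that far. Criterion e) admits conditions, not their drugs, and the weight-related exclusions may remove some metabolic drugs. Criterion f) does not say whether it means past or present use, and the population sentence suggests hormone therapy has already been undergone. This stands as a limit on wording. It also means that current use is undefined, which is a reason to record it.

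**A stable drug cancels in Δ.** This is correct, and it removes the simplest route to bias. An effect of 0.5 to 1.0 SD on Δ is a sizeable modification of training response, and nothing in the documents supports that magnitude. The point survives because no stability rule is stated and because the SAP does not commit to Δ for the group comparison.

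**The error rates can be made to look worse.** If SD is read as total within-group SD, the noncentral t (28 df) gives 5.8%, 8.3% and 18.5% for biases of 0.1, 0.2 and 0.4 SD. Those figures leave no separate allowance for the variance that drug use adds. A flat claim that the error exceeds 5% is also too strong, since at 9 v 6 users it barely moves.

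**A systematic link is not documented.** One might infer that tumour type or stage drives both chemotherapy amount and hormonal therapy. The documents do not say so. They establish only that allocation cannot prevent such a link.

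**Drugs are one confounder among many.** Age, disease stage and time since treatment could differ in the same way, and the between-group test is itself poorly specified, because paired or unpaired testing is chosen by normality. Both remarks are right. They argue for labelling the contrast observational and defining the test first, with drug adjustment as a sensitivity analysis rather than a cure.

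**Conclusion.** The concern holds in a conditional form. The exposure contrast cannot be protected by randomisation, hormonal therapy is left open at entry, and no planned analysis adjusts for anything. A difference in Δ could then be misattributed to chemotherapy exposure if drug use differs between groups and either modifies the response to training or changes during the 6 weeks. If post values are compared, the drug's full effect on level enters too.

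Under the stated assumptions the harm is negligible at a 20-point gap and material at about 33 points or more. These are illustrations, since neither drug shares nor drug effects are in the documents. The documents do not show that bias is present. They show that the plan could neither detect it nor allow for it. The change is cheap and should be made, with medium confidence in the practical importance.

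**What to change.** 1. State in the SAP that the between-group result for each main vascular outcome is a linear model of Δ on group and the baseline value of that outcome, reported as the adjusted difference with its 95% CI.
2. Pre-specify a sensitivity model adding current hormonal therapy (yes/no), and one adding current antihypertensive use (yes/no).
3. Record both variables at baseline, note any change by follow-up, and tabulate them by group.
4. Describe the EG-HCHT versus EG-LCHT contrast as observational. Adjusting for one or two drugs does not make it causal.
5. Reconcile criterion f) with the Methods sentence that women have been through all treatment stages including hormone therapy, so that it is clear what is being recorded.

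**Cost.** This needs SAP wording and two yes/no variables close to what screening against criteria e) and f) already touches. The hormonal-therapy term raises the SE of the group difference by about 2% to 10% for gaps of 20 to 40 points, and by 25% at 12 v 3 users, before any gain in precision from the baseline value. The second drug term costs more; that cost was not calculated. With 30 women, some drug-by-group cells may be sparse, which is why the drug-adjusted models belong in sensitivity analyses.

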
16. Cohen J. *Statistical Power Analysis for the Behavioral Sciences*. 2013.

STATISTICAL ANALYSIS PLAN (SAP): Data will be presented as the mean \pm standard deviation (SD). Normality and homoscedasticity assumptions will be tested by using Shapiro-Wilk tests and homoscedasticity by the Levene test. For those outcomes with normal distribution, paired *t*-test was applied to test differences, while to those with no normal distribution, unpaired *t*-test was applied. Cohen's *d* effect size (<0.2 = negligible, $0.2-0.49$ = small, $0.5-0.79$ = moderate, ≥ 0.8 = large) for interactions that showed statistically significant (16). Each delta (Δ), pre-post changes, of main and secondary outcomes will be calculated in all groups. To test the associations among main vascular outcomes (PWV, FMD, cIMT_{av}, cIMT_{max}) with anthropometric, body composition, metabolic, cardio-vascular outcomes, and physical fitness outcomes, simple linear regression (to parametric) with R² prediction percentage, or the *Rho* Spearman nonparametric correlation (r_s =) will be applied. Statistical analyses will be developed using Prism 8.0 software (Graph Pad, San Diego, CA, United States), and the SPSSTM software 29 version for Windows (IBM SPSS Inc., Chicago, IL, USA). The alpha level will be fixed at ($P \leq 0.05$) for all statistical significance.

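### The SAP plans no confidence intervals and reports effect sizes only for significant results, so a non-significant high-versus-low comparison at 15 per group comes with no statement of the differences it leaves open

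*Combined protocol and SAP*

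**What the plan says.** The Statistical Analysis Plan (SAP) is a single paragraph. For the effect questions it provides four outputs:

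- A descriptive summary: "Data will be presented as the mean" ± SD. No alternative is given for outcomes that fail the normality check, although the SAP sorts outcomes by that check when it chooses tests.
- Change scores: "pre-post changes, of main and secondary outcomes will be calculated in all groups". Nothing is said about an interval for them.
- A significance rule: "The alpha level will be fixed at" P ≤ 0.05 for every test.
- Cohen's d, but only "for interactions that showed statistically significant (16").

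R² and Spearman's rho are planned for associations, not for training effects or group comparisons. The combined document contains no confidence interval, equivalence margin, power statement or sample-size rationale.

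The Methods name two groups, both of which train: "experimental group of high chemotherapy exposure (EG-HCHT, n=15") and "experimental group of low chemotherapy exposure (EG-LCHT, n=15"). The general objective concerns effects "in female breast cancer survivors who received lower" (≤ 7 sessions) and higher (≥ 8 sessions) amounts of chemotherapy.

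**The concern.** Because both groups train, the difference in Δ between them is the only between-group comparison that the design offers. In a design with two groups and two time points, that difference is also the group-by-time interaction, which is presumably what the Cohen's d sentence has in mind.

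Under the SAP's rule, a significant result is reported with a P value and an effect size. A non-significant one is reported with a P value alone. That leaves the plan silent where a reader most needs to know whether the data point to a small difference or are simply too few to tell. It also means that the published effect sizes would be those selected by significance, which in small samples tend to be the larger ones.

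Mean ± SD for everything is a lesser, related problem. For an outcome that the SAP has itself classed as non-normal, the mean and SD may describe the data poorly, and the plan has nothing to put in their place.

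**Working it through.** The plan gives no precision or power figure, so there is nothing of its own to reproduce. The check is how wide the missing intervals would be.

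**Inputs from the documents.** 15 women per group (Methods); alpha 0.05 (SAP); the SAP's effect-size scale, with 0.5 to 0.79 moderate and 0.8 or more large.

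**Assumptions.** Two-sided testing (sidedness is not stated). An unpaired t comparison of Δ with a common SD (the SAP does not clearly assign a test to this contrast). No dropout. Results are in units of the SD of Δ, because no outcome SD is given.

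**Group difference in Δ.** Half-width = t(0.975, 28) × √(1/15 + 1/15) = 2.048 × 0.365 = 0.748 SD of Δ.

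**Change within one group.** Half-width = t(0.975, 14) / √15 = 2.145 / 3.873 = 0.554 SD of Δ.

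**What a non-significant difference leaves open** (observed difference ± 0.748):

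| Observed difference (SD of Δ) | 95% CI (SD of Δ) |
|---|---|
| 0 | −0.75 to +0.75 |
| 0.20 | −0.55 to +0.95 |
| 0.50 | −0.25 to +1.25 |
| 0.74 | −0.01 to +1.49 |

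All four are non-significant. The ±0.75 figure applies only when the observed difference is zero; in the other rows the interval reaches further in one direction. On the SAP's own scale, 0.75 lies within moderate and 1.49 is well into large.

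**Power at 15 per group (noncentral t).** A true difference of 0.5 SD of Δ is significant in 26% of trials and missed in 74%. A true difference of 0.8 SD is significant in 56% and missed in 44%. About 1.06 SD would be needed for 80% power.

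**Sensitivity to dropout.** The half-width for the group difference rises to 0.777 SD with 14 per group, 0.847 with 12 and 0.940 with 10.

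**Units.** If the pre-post correlation is 0.5 to 0.9 (an assumption; the documents give none), the SD of Δ is √(2(1 − r)) times the raw SD, which is 1.00 to 0.447. In raw-SD units, ±0.748 SD of Δ is then about ±0.75 to ±0.33.

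**The case against.** The best defence is that the precision is not lost, only not printed. The SAP calculates Δ for main and secondary outcomes in all groups and presents data as mean ± SD, so the natural reading is that Δ will be shown as mean ± SD per group. With 15 per group a reader could then compute the interval as the difference in mean Δ ± 2.048 × √((SD₁² + SD₂²)/15). This stands, and it makes the point one of reporting. A reader might infer that the SD of Δ could not be recovered from the planned tables; the documents do not support that. Leaving the calculation to readers is still a weak substitute for reporting it, and it does not help where mean ± SD is a poor summary.

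A second defence is that the SAP nowhere says it will treat P > 0.05 as proof of an equal response. That is also right. A reader might infer that the trial intends an equivalence claim, but the text contains none, and the objective can be read as asking about effects within each exposure group. What stands is narrower: nothing in the plan guards against that interpretation. For the same reason, a similarity margin for every outcome would be a debatable extra in a trial that claims no equivalence.

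Third, it is tempting to say that non-significance is the most likely result at this size. That depends on the unknown true difference; at 0.8 SD of Δ, significance is slightly more likely than not.

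Finally, intervals would not settle other questions about this contrast, such as which test applies to it, or how women can be randomised to groups defined by past chemotherapy. Those are separate points.

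**Conclusion.** The point holds as a minor one. The significance-gated effect-size rule is explicit in the SAP, and no interval is planned anywhere, so a non-significant comparison is left with a P value alone. The size of what goes unreported is a half-width of about 0.75 SD of Δ for the group difference and 0.55 SD of Δ for a within-group change. These figures rest on two-sided unpaired analysis (paired for the within-group change) and full retention of 15 per group; losses would widen them. The mismatch between a mean ± SD format for all data and the SAP's own class of non-normal outcomes also stands, although the documents do not say which outcomes will fall in that class, so its effect cannot be sized.

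The documents do not show that the sponsor will draw a conclusion of equal response. The finding is that the plan does not prevent one and does not report what a reader would need to judge it.

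**What to change.** Keep the SAP's opening sentence, since it is the only provision for describing the data, and add after it:

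> For every main and secondary outcome, whatever its P value, the mean Δ with 95% CI will be reported in each group, together with the EG-HCHT minus EG-LCHT difference in Δ with 95% CI. Cohen's d will be reported for all comparisons, not only significant ones. A non-significant difference will not be interpreted as an equal response. Outcomes classed as non-normal will be shown as median and interquartile range, with the Hodges-Lehmann estimate and its 95% CI.

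The existing limit of Cohen's d to significant interactions should be deleted so that the two statements do not conflict.

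The cost is SAP wording and slightly longer tables, with no new data, participants or visits. The downside is that many high-versus-low results may be visibly inconclusive, which is a fair description of what 15 against 15 can show.

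### Levene's test is planned with no stated consequence and the version of the unpaired t-test is left open; Welch should be pre-specified for the comparison of change between exposure groups

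*Combined protocol and SAP*

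**What the plan says.** The Statistical Analysis Plan opens with its assumption checks: "Normality and homoscedasticity assumptions will be tested by using Shapiro-Wilk tests and homoscedasticity by the Levene test". No threshold or consequence is attached to the second of these, "homoscedasticity by the Levene test".

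The next sentence chooses the test by normality alone: "For those outcomes with normal distribution, paired *t*-test was applied to test differences", "while to those with no normal distribution, unpaired *t*-test was applied". Neither the pooled nor the Welch version is named, and naming SPSS and Prism does not settle it. Pre-post deltas are to be calculated in all groups, but no test is named for comparing them between groups and no confidence interval is planned. On significance the SAP says "The alpha level will be fixed at" 0.05; sidedness is not stated.

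The Methods name "an experimental group of high chemotherapy exposure (EG-HCHT, n=15" and a low-exposure group (EG-LCHT) of the same size. The general objective defines the groups by chemotherapy received, at most 7 sessions or at least 8. The documents give no SDs, no dropout allowance and no rule for incomplete follow-up.

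**The concern.** A planned assumption check should lead somewhere. Of the two t-tests named, only the pooled unpaired test needs equal group variances. The paired test works on within-woman differences and does not. So Levene's test bears only on a between-group comparison, and there the SAP leaves the choice of version open until the data have been seen.

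Equal variances cannot be taken for granted. The groups are labelled by a patient characteristic, past exposure, so even with equal mean responses nothing in the design makes the spread of change equal. Equal completion cannot be taken for granted either, since women are recruited from community groups and attrition is not discussed.

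At stake are the error rate of the high-versus-low comparison and the coverage of any interval reported with it. Either can be off in both directions.

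**Working it through.** The plan gives no power, SD or dropout figure to reproduce. The only figure to check against is the nominal alpha of 0.05, taken here as two-sided.

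**Inputs.** From the Methods: 15 and 15 planned. Assumed: uneven completion (15 v 12, 15 v 10), SD ratios of 1.5, 2 and 3, and normally distributed changes unless stated otherwise.

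**Why uneven sizes matter.** The pooled test estimates the variance of the mean difference as s_p² × (1/n1 + 1/n2), with s_p² = [(n1−1)s1² + (n2−1)s2²] / (n1+n2−2). The true variance is σ1²/n1 + σ2²/n2. Putting the true SDs into both:

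- 15 v 15, SDs 1 and 2: s_p² = (14×1 + 14×4)/28 = 2.5. Pooled 2.5 × 2/15 = 0.333; true 1/15 + 4/15 = 0.333. They agree, and only the degrees of freedom are slightly too generous.
- 15 v 10, smaller group more variable: s_p² = (14×1 + 9×4)/23 = 2.174. Pooled 2.174 × (1/15 + 1/10) = 0.362; true 1/15 + 4/10 = 0.467. The standard error is √(0.362/0.467) = 0.88 of its proper size.
- 15 v 10, larger group more variable: s_p² = (14×4 + 9×1)/23 = 2.826. Pooled 0.471; true 4/15 + 1/10 = 0.367. The standard error is √(0.471/0.367) = 1.13 of its proper size.

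**Type I error of the pooled test**, simulated with 400,000 normal-data trials per scenario:

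| Completers | More variable group | SD ratio 1.5 | SD ratio 2 | SD ratio 3 |
|---|---|---|---|---|
| 15 v 15 | either | 5.1% | 5.4% | 5.6% |
| 15 v 12 | smaller | 6.1% | 7.1% | 8.1% |
| 15 v 12 | larger | 4.3% | 3.9% | 3.7% |
| 15 v 10 | smaller | 7.1% | 8.7% | 10.6% |
| 15 v 10 | larger | 3.6% | 3.0% | 2.6% |

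Welch's test stayed between 4.9% and 5.2% in all of these. Coverage of a pooled 95% interval is 100% minus the tabled value, so at 15 v 10 with SD ratio 2 it is 91.3% or 97.0%.

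**Levene as a gate.** Mean-centred Levene's test at 15 v 15 detects an SD ratio of 1.5 in about 27% of trials and a ratio of 2 in about 61%. Using Welch only when Levene is significant gives, at SD ratio 2, 5.1% at 15 v 15, 5.8% at 15 v 12 and about 6.6% at 15 v 10 (smaller group more variable). The gate removes part of the excess and leaves the rest.

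**Skewed data.** At 15 v 10 with SD ratio 2 and the smaller group more variable, exponential data give pooled 9.7% and Welch about 7.8%; lognormal data give pooled 11.1% and Welch about 10.5%. For lognormal data at SD ratio 1.5 Welch is slightly worse (7.2% v 6.8%).

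**Cost in power** with equal variances and a true difference of 0.8 SD: 56.4% pooled v 56.1% Welch at 15 v 15 (0.3 points); 46.8% v 45.9% at 15 v 10 (0.9 points).

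**The case against.** A reader might infer that the equal-variance t-test will be used whatever Levene shows. The documents do not support that: the SAP says only that the test is unpaired. A variance test planned alongside SPSS can as readily be read as the means of choosing between the pooled and Welch results. On that reading the excess at 15 v 10 with SD ratio 2 falls from 8.7% to about 6.6%. This objection stands against the stronger inference, but the gating rule is unwritten and only partly effective.

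Nor does the SAP tie an unpaired test to the high-versus-low comparison. Read literally, it is the fallback for non-normal outcomes, and those are where Welch helps least. This also stands. A between-group comparison is nevertheless clearly intended: the objective refers to lower and higher chemotherapy exposure, deltas are calculated in all groups, and effect sizes are promised for interactions. With two groups and two time points, the interaction is the unpaired comparison of deltas.

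A third inference would be that the higher-exposure group is the more variable because its session count has no upper limit. That describes the spread of exposure, not of change in the vascular outcomes. The inclusion criteria also admit women without chemotherapy, so the low group may be mixed. The direction of any drift is therefore unknown.

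Finally, at 15 v 15 the effect is negligible. That is correct and limits the weight of the point.

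**Conclusion.** The point holds as a minor one. Levene's test has no stated consequence, and the version of the unpaired t-test is unspecified. At the planned sizes the pooled test exceeds its nominal 5% by about 0.1 to 0.6 percentage points. A material distortion needs uneven completion and unequal variances together, neither of which the documents project or rule out; whether the test then rejects too often or too rarely depends on which group is more variable. Unconditional Welch removes the problem for roughly normal changes but not for strongly skewed ones.

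Choosing between a paired and an unpaired test by normality, in the same part of the SAP, is the larger defect: pairing follows from the design, and an unpaired t-test is not a remedy for non-normality. The present point is best settled when that sentence is rewritten.

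**What to change.** Drop Levene's test as a gate. State that pre-post comparisons within a group use a paired test and that between-group comparisons use an unpaired one. For EG-HCHT versus EG-LCHT, name Welch's unequal-variance t-test on Δ, reported with its 95% CI whatever a variance test shows. In SPSS this is the row for equal variances not assumed; in Prism it is the Welch option.

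The variance choice itself is one sentence, but it has to sit within the rewritten test-selection rule, because the SAP at present names no between-group test of Δ and no interval. The statistical cost, if variances are in fact equal, is about 0.3 points of power at 15 v 15 and 0.9 at 15 v 10. Strongly skewed outcomes need separate thought: at 15 v 10 with a twofold SD ratio, Welch's error rate was still about 8% to 10% for the skewed shapes tried.
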